Pathophysiological support for these conclusions comes from our studies (Schobel et al, Neuron, 2013) in which we applied fMRI indicators of metabolism and volumetric MRI to patients in prodromal stages of the disease who then progressed to the psychotic stage, and to a mouse model of the disease. Collectively, these studies suggested that glutamate is a driver of hippocampal dysfunction, that fMRI measures are sensitive to glutamate elevations, and that glutamate-reducing drugs can ameliorate hippocampal

dysfunction. We also have completed preliminary studies using magnetic resonance spectroscopy, in which we show that hippocampal glutamate is elevated in prodromal stages of the disease.

Based on the results of these and other studies, we have recently proposed a mechanistic model of disease progression (Small, Neuron, 2014), which predicts that because of its distinct pathophysiological features the prodromal stage of disease is a unique time-window that is most amenable to glutamate-reducing interventions. This mechanistic model motivates this protocol in which we hypothesize that: 1) MRI based measures of hippocampal metabolism and glutamate can be used as in vivo biomarkers of target engagement when using a glutamate-reducing intervention. 2) Glutamate-reducing interventions will be most effective when administered to prodromal patients, and only when they are shown to engage their target. The R61 phase of this proposal is designed to test the first hypothesis, and the R33 phase is designed to the second. The current IRB describes the R61 phase.

We will also perform a study to examine the stability of our MRI measures over up to 4 months in a healthy control population.

Specific Aims and Hypotheses

Specific Aims and Hypotheses

To perform a double-blind, randomized, phase Ib, multiple dose trial of 14 days of treatment with POMA (40mg bid, 80mg bid, 120mg bid, 160mg bid) in clinical high risk patients to determine which dose, if any, reduces hippocampal glutamate and metabolism using MRI techniques. The GO NO-GO decision will be whether or not any dose tested in the R61 phase of the trial decreases left CA1 CBV.

To examine the stability of our MRI measures over up to 4 months in a healthy control population.

Description of Subject Population

Sample #1

Specify subject population

Clinical High Risk

Number of completers required to accomplish study aims

12

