Projected number of subjects who will be enrolled to obtain required number of completers

50

Age range of subject population

18-30

Sample #2

Specify subject population

Controls

Number of completers required to accomplish study aims

20

Projected number of subjects who will be enrolled to obtain required number of completers

30

Age range of subject population

18-30

Gender, Racial and Ethnic Breakdown

33% Caucasian, 33% African American, 10% Asian, 24% Mixed; 33% Hispanic; 70% male, 30% female

Description of subject population

As above

Recruitment Procedures

Describe settings where recruitment will occur

Patients will be told about the study by staff at the COPE clinic (IRB #6654R). If they are interested, they will then be referred to study investigators designated to obtain informed consent, who will describe the study in greater detail and then obtain informed consent. Specifically, patients interested in participation will be screened by study physicians and told about the study. They will be told about the procedures and risks, that the study involves randomization and the details will be explained. They will also be told that participation is voluntary, and of the extra study details beyond that of the COPE protocol itself and affiliated observational studies, including exposure to POMA and gadolinium contrast. If interested and eligible, patients will have an evaluation of their capacity to consent and invited to provide written informed consent.

Healthy control subjects will be recruited through #6654R as well as from other Area Psychosis research studies that include healthy control subjects who have expressed interest in additional research.

How and by whom will subjects be approached and/or recruited?

See above. All patients will be initially recruited through 6654R.

How will the study be advertised/publicized?

As above. Patients are initially recruited through 6654R.

Do you have ads/recruitment material requiring review at this time?

No

Does this study involve a clinical trial?

Yes

Please provide the NCT Registration Number

NCT03321617

Concurrent Research Studies

Will subjects in this study participate in or be recruited from other studies?

Yes

Describe concurrent research involvement

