We will obtain blood samples for PK testing of POMA on days 7 **2-3 hours after the dose and 14 right before the MRI scan.**

Phone Check Ins

Study physicians will perform phone check ins between days 1 and 7 and between days 8 and 14. **In addition, research staff will observe patients taking each of their doses via hipaa compliant video.**

Stand By

We will give all subjects the option of being a standby subject. Standby subjects will be asked to come in on a day when a brain scan is scheduled for another participant. If for some reason the original participant does

not complete the imaging procedures, the standby will be asked to participate in the imaging procedures in place of that person. If the original participant does complete the imaging procedures, they standby will be sent home. We expect that standbys will have to wait between 1-3 hours as a standby participant. Subjects can choose to be a standby subject by checking one of the boxes found at the end of the consent form. We may ask standbys to be standby subjects multiple times. In addition, we may schedule more than one standby for a given day.

We have attached a table that includes a summary of all procedures.

This trial will be monitored by a DSMB

Healthy Control Test Retest Study

Healthy control subjects will be screened with the SCID as well as a urine toxicology and urine pregnancy test. Eligible subjects will receive up to 4x1 hour MRI/MRS scans over a 4 month period. MRI scans will be done as described above, without gadolinium. Standby procedures will also apply to healthy control subjects.

Remote Procedures: Some of the visits may be conducted remotely using the telephone or HIPAA-compliant video teleconferencing. In particular, all procedures that can be done remotely including consent, capacity and clinical/behavioral assessments will be done remotely except for the blood draw and physical exam which will have to occur separate from MRI since these screening procedures are required before we begin the study (technically not required for MRI but we prefer to know if someone will be eligible for the study before we have people do MRI; we will submit individual exception requests if we want to perform an MRI without having received the results of labs and physical exam).

I attest to follow the COVID-19 Safety Guidelines for Columbia Psychiatry and NYSPI Re-Entry outlined in the NYSPI Director's June 1st memo, which include but are not limited to:

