COVER PAGE

STATISTICAL ANALYSIS PLAN

OFFICIAL TITLE: Glutamate Reducing Interventions in Schizophrenia

NCT NUMBER: NCT03321617

DATE OF DOCUMENT: September 2, 2021

Statistical Analysis

Sample size and randomization: For the sample (n=3 subjects per 4 doses) the randomization sequences will be balanced in blocks of 4.

Primary outcome: Change (hypothesized decrease) in left CA1 CBV from baseline to 14 days.
Adherence, dropouts, and missing data: As this is a dose finding trial it is highly important that analyses be done on subjects who adhere closely to taking the study drug across the 14 days and who have complete data. We have set a threshold of adherence at >80% compliance. Subjects who are non-adherent, dropout, or who have unusable CA1 values at baseline or 14 days will be replaced.

Hypothesis testing (Go No-Go Criteria): The hypothesis to be tested is that at least one of the 4 doses shows a mean decrease in left CA1 CBV from baseline to 14 days of at least 0.33 standard deviations. Given that this is a dose finding study, to confirm the hypothesis we will not require a statistically significant test (e.g. $p < .05$), but instead will require the estimated mean decrease across the 3 patients in any one dose to be at least 0.33 standard deviations (standardized change will be used as the effect size measure). One-way ANOVA of the change scores on the 4 dose levels will be used to estimate the mean changes for each dose level standardized by the pooled standard deviation of change. Based on our prior data, the test-retest reliability of CA1 CBV (taken across 3 weeks in 4 patients on placebo) is very high (ICC = 0.85) providing confidence in the specificity of our measure of change and justification for including 3 patients at each level.

The target mean decrease of 0.33 standard deviations was chosen based on: 1) it represents half of the difference found between healthy controls and CHR patients in previous work and 2) we expect any decrease in CA1 CBV to be related to improvement in symptoms given our finding of a linear relationship between CA1 CBV and symptoms in CHR.

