Similar analyses will be conducted for our secondary measures of hippocampal Glx (MRS). The clinical symptoms (SIPS) and cognitive measures (Matrics) are measured at 7 and 14 days and will be modeled with repeated measures ANOVA summarizing average change by dose over the study period. The safety measures (e.g. side effects) will be measured similarly throughout the study and will similarly be modeled with repeated measures ANOVA providing estimates at each time point and also aggregated across the study.

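### The SAP gives Glx, SIPS and MATRICS no analysis set of their own; its one evaluability rule is tied to CA1 CBV, so usable secondary data may go unanalysed and only CBV is secured at 3 per dose

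*SAP*

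**What the plan says.** The SAP (Statistical Analysis, sample size paragraph) plans 3 patients at each of 4 doses: "For the sample (n=3 subjects per 4 doses) the randomization sequences will be balanced in blocks of 4". Its paragraph on adherence, dropouts and missing data asks that "analyses be done on subjects who adhere closely to taking the study drug across the 14 days and who have complete data", sets the adherence threshold at more than 80%, and continues: "Subjects who are non-adherent, dropout, or who have unusable CA1 values at baseline or 14 days will be replaced". Of the three replacement triggers, the CA1 one is the only one about data quality.

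The closing paragraph covers the secondary outcomes. For Glx it says "Similar analyses will be conducted for our secondary measures of hippocampal Glx (MRS"). SIPS and MATRICS, rated at days 7 and 14, "will be modeled with repeated measures ANOVA summarizing average change by dose over the study period". It does not define complete data outcome by outcome, and it does not say what happens to the spectra and ratings of a replaced patient.

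In the protocol (Study Procedures), contrast MRI and MRS are listed as one session of one hour. Day 7 repeats the baseline measures except the SCID and MRI. Day 14 repeats them again with the MRI, without the SCID and the DNA blood sample. For the control test-retest study, which includes MRS, "MRI scans will be done as described above, without gadolinium". Under Criteria for Early Discontinuation, staff are to seek final scans and ratings from patients who stop early; neither document says how those data are used.

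**The concern.** A condition on CA1 usability makes sense for the CBV analysis. It has no clear purpose for an outcome that does not use the CBV map. An adherent patient whose CA1 value fails can still have a baseline and day-14 spectrum and three sets of SIPS and MATRICS ratings. If the complete-data condition is applied as one global rule, none of this is analysed.

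The rule also fails to protect the secondary outcomes. An unusable spectrum or a missed rating does not lead to replacement, so only CBV is assured of 3 patients per dose. A classical repeated measures ANOVA needs every visit, so one missed rating can remove a patient.

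Glx is the trial's MRS readout of the glutamate half of the protocol's aim. With groups this small, one inclusion decision can move a dose mean noticeably, and the SAP as written allows two analysts to build different Glx, SIPS and MATRICS data sets.

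**Working it through.** **Planned sample.** 3 per dose × 4 doses = 12. This matches the 12 entered in the protocol (Description of Subject Population) under "Number of completers required to accomplish study aims". There is no power or alpha figure to reproduce, because the SAP requires no significance test.

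**Precision as planned.** In units of the SD of change, the standard error (SE) of a dose mean is 1/√n. At n = 3 it is 0.577. With the pooled SD on 12 − 4 = 8 df, the 95% half-width is 1.33 SD.

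**Inputs that must be assumed.** Neither document gives a rate of unusable CA1 values, unusable spectra or missed ratings. The protocol projects 50 patients under "Projected number of subjects who will be enrolled to obtain required number of completers", but the step from 50 to 12 mixes screening failure, non-adherence, dropout and scan failure, so no rate can be taken from it.

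**Records forgone through the CA1 condition.** Let u be the share of adherent completers with an unusable CA1 value. Reaching 12 CBV-evaluable patients then takes on average 12/(1 − u) adherent completers. If all of them enter the secondary analyses, evenly over doses, the SE ratio against the CA1-selected set is √(1 − u).

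| u (assumed) | Completers, 12/(1 − u) | Extra records | Mean n per dose | SE of dose mean | SE ratio | Reduction |
|---|---|---|---|---|---|---|
| 10% | 13.3 | 1.3 | 3.33 | 0.548 | 0.949 | 5% |
| 20% | 15.0 | 3.0 | 3.75 | 0.516 | 0.894 | 11% |
| 30% | 17.1 | 5.1 | 4.29 | 0.483 | 0.837 | 16% |

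This assumes that every extra patient has usable secondary data. It is an upper bound for Glx, because CBV and MRS share a session and may fail together. It counts only patients who reach day 14; someone who goes no further after an unusable baseline scan leaves nothing to recover.

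**Unusable spectra in patients who are not replaced.** One loss takes a dose from 3 to 2 pairs: the SE goes from 1/√3 = 0.577 to 1/√2 = 0.707, a ratio of √(3/2) = 1.22, or 22% wider. If a share f of the 12 CA1-usable patients has an unusable spectrum, independently between patients, the chance that some dose has fewer than 3 pairs is 1 − (1 − f)^12: 46% at f = 5%, 72% at 10%, 93% at 20%.

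**Missed ratings.** If a share m of the 12 patients lacks a day-7 or day-14 rating and incomplete cases are dropped, the chance of losing at least one patient is 1 − (1 − m)^12: 46% at m = 5% and 72% at m = 10%. The SAP does not state that incomplete cases are dropped; this follows from the classical form of the named method.

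**The case against.** The strongest reply is that the SAP says *replaced*, not discarded. Replacement secures 3 per dose for the Go decision, and no sentence orders that the replaced patient's spectra or ratings be thrown away. That is correct. A reader might infer that the SAP drops good spectra and keeps bad ones, but the documents support neither as a stated rule. The two halves even need opposite readings of complete data: a global reading would exclude a patient with a bad spectrum, and a reading per outcome would retain a good one. An unusable spectrum also yields no change score, so there is nothing to keep.

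Two further inferences fail. The wording about similar analyses covers Glx only; SIPS and MATRICS have their own sentence and model, so any carry-over to them comes from the general complete-data sentence. And a record lost through CA1 replacement is not a third of a dose group. The replacement restores the planned 3, so that record would be additional.

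It is also fair that a shared cause such as movement could spoil both CBV and MRS, and that contrast-free control scans do not show that CA1 failures are specific to contrast. Missing the whole day-7 or day-14 visit would usually fall under an existing trigger, which leaves mainly the single instrument missed in a patient who otherwise continues. A common set for all outcomes is defensible where CBV change is to be related to symptoms.

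What stands after this is the gap itself: neither reading is written down, the secondary outcomes have no rule of their own, and the most natural reading leaves usable data out.

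**Conclusion.** The concern holds as a gap in the definition of the analysis sets, with a modest and conditional cost. On the most natural reading, secondary data from CA1-replaced patients go unanalysed. This forgoes about 5% to 16% of the SE of a dose mean, relative to using every usable patient and not relative to the planned 3 per dose. The range rests on assumed CA1 failure rates of 10% to 30% and is a ceiling for Glx. The loss that can take an outcome below plan comes from an unreplaced patient with an unusable spectrum (22% wider SE for that dose) or from case-wise deletion after a missed rating.

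Severity is minor. A reader might infer that the dose decision is at risk, but Go/No-Go rests on left CA1 CBV alone, and its set is sound on this point. Only secondary estimates change, and they are imprecise in any case at 3 per dose.

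**What to change.** Add a short passage to the SAP that does the following:

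- Applies the CA1-usability condition to the CBV analysis only.
- Analyses Glx in all adherent patients with usable spectra at baseline and day 14, including patients replaced for unusable CA1 values.
- Analyses SIPS and MATRICS in all adherent patients with a baseline and at least one later rating, again including patients replaced for unusable CA1 values.
- Fits SIPS and MATRICS with a linear mixed model (dose, visit, dose by visit, random patient effect) in place of repeated measures ANOVA, so that one missed rating does not remove a patient.
- Reports n per dose for each outcome.

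The cost is a few sentences, with no new patients, scans or ratings. The CBV Go/No-Go set stays as it is. The small downside is that n will differ between outcomes and doses, so each table must carry its own counts. Where CBV change is related to symptoms, the patients with both measures can be used and labelled as such.
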